## **9.6. Imaging**

### **9.6.1. Zr-GSK2398852 PET**

Subjects will participate in up to two dosing sessions, each associated with the administration of up to 37 MBq Zr-GSK2398852 and up to 3 PET scans within approximately 5 days after the administration of radioactivity. The PET scan times for

each of the dosing sessions of the first patient are listed in Section 5.3.1. These times may then be varied for subsequent patients.

For each dosing session, the  $^{89}\text{Zr}$ -GSK2398852 (37 MBq radioactivity and a mass dose of 10 mg) will be administered IV in a room separate from the PET camera room. After a defined waiting time (defined by the time of the first PET scan) the patient will be taken to the PET camera room and placed in comfortable position on the PET couch. Arms are stretched over the head.

A low-dose CT scan is made for orientation of the heart and a PET acquisition of 4-5 scans of about 20 minutes is started. This can be associated with cardiac gating if feasible.

Thereafter a whole body (head to upper thighs) low dose CT scan is made for anatomical orientation and for attenuation correction.

Sequential PET acquisitions will be made with about 3-5 minutes per bed position, covering the head to the upper thigh. The duration is of the order of 45 minutes.

The total duration of the scanning procedure is expected to be less than 2 hours.

Further details on scanning procedure are provided in a dedicated Image Acquisition and Analysis Manual.

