#### **3.4.2. Radiation exposure**

The study will involve radiation exposure from up to 2 separate administrations of  $^{89}\text{Zr}$  labelled anti-SAP ( $^{89}\text{Zr}$ -GSK2398852) to patients, each associated with 3 low-dose whole-body CT imaging scans, plus potential PET procedures with PiB and WAT.

In oncology  $^{89}\text{Zr}$ -labelled mAb studies, a minimum administration of 37 MBq is regarded as adequate for good image quality. In some studies, this administration has been repeated up to 3 times. Some of the studies have been associated with other PET studies, notably Fludeoxyglucose (FDG). The studies conducted in the United States (US) have

typically been associated with much higher administrated doses such as 185 MBq [[Pendit-Taskar 2014](#), [Ulaner 2016](#)].

The prognosis of ATTR-CM is similar to that of metastatic cancers, in that the life expectancy is less than 4 years from diagnosis, and the older age at presentation for wild-type ATTR (median 75 years), means that the subjects can be exposed to higher levels of radiation without significantly increasing the risk of developing secondary tumors [[Shuryak 2010](#)].

Based on the above information and rationales, the proposed  $^{89}\text{Zr}$ -GSK2398852 dose is approximately 37 MBq for each administration, 2 dosing sessions per subject, with a total of approximately 74 MBq. The mean effective dose for  $^{89}\text{Zr}$ -mAb PET study was reported to be 0.53 mSv/MBq [[Börjesson 2009](#)], hence 37 MBq of  $^{89}\text{Zr}$ -GSK3128349 in this study would provide approximately 19.61 mSv (37 MBq x 0.53 mSv/MBq) of exposure, which together with the low-dose CT scans (0.5 mSv/CT scan x 3 CT scans) yield approximately 21.11 mSv. The single PiB procedure including its CT component is expected to add 1.5 mSv, and the two WAT procedures to add a total of 1 mSv in radiation exposure.

Total radiation dose exposure per subject is therefore expected to be a maximum of up to 44.7 mSv. With some residual radioactivity in the injection syringe and considering radioactive decay till time of injection, we will aim to be below 44 mSv across the study. Reference [Appendix 9](#) for additional information.

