
Subjects exposed to ionising radiation as a consequence of participation in this study (e.g. Zr-GSK2398852 imaging).
	
Ionising radiation exposure from PET scanning comes from the administered radioligand and CT examination. The total radiation burden per subject is calculated as 21.1 mSv per Zr-GSK2398852 scan session; and the single PiB and two WAT scans together 2.5 mSv; up to total 44.7 mSv for all PET scans and this corresponds to a lifetime risk of a fatal malignancy of about 1 in 600 [ICRP 2007].
 
Subjects who participate will receive a radiation exposure up to a maximum of 44.7 mSv across two separate dosing sessions.
 
The ceiling radiation exposure of 44.7 mSv is judged as safe to the individual, and justified on a trial basis due to the clinically severe and life-limiting nature of ATTR cardiomyopathy, and the importance to the study objectives of optimising the signal-noise ratio from the myocardium during each PET scan
	
The study has been designed to keep the radiation dose as low as reasonably practicable (ALARP) whilst obtaining images of sufficient quality to meet the objectives.
 
Subjects <65 years of age will not be eligible
 
The study will exclude women of childbearing potential.
 
Subjects who have been exposed to ionising radiation in excess of 10 mSv above background over the previous three-year period as a result of occupational exposure to radiation or as a result of research studies are excluded. Clinically justified (therapeutic or diagnostic) exposures are not included in the exposure calculation. Subjects are asked about any occupational exposure or previous participation in research studies at screening so that dose estimates can be obtained where necessary.

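### The 44.7 mSv maximum omits the heart CT in the PET procedure, the risk table's 1 in 600 does not follow from the protocol's 5.5% per Sv, and the 10 mSv prior-exposure exclusion is missing from Section 6.2

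*Protocol*

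**What the plan says.** **Dose.** Protocol Section 3.4.2 describes up to two 89Zr administrations, "each associated with 3 low-dose whole-body CT imaging scans". It takes 19.61 mSv per 37 MBq administration, adds three CTs at 0.5 mSv, and then adds 1.5 mSv for PiB and 1 mSv for two WAT scans. It concludes: "Total radiation dose exposure per subject is therefore expected to be a maximum of up to 44.7 mSv". Allowing for syringe residue and decay, it adds: "we will aim to be below 44 mSv across the study". Section 3.4.3 calls the same figure a ceiling ("The ceiling radiation exposure of 44.7 mSv is judged as safe to the individual"), and Section 3.4.5 repeats it as a maximum. Appendix 9 gives the same sum and permits a second low-dose CT if the subject has to be repositioned.

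**Procedure.** Section 9.6.1 has two CTs. The first precedes the cardiac acquisition: "A low-dose CT scan is made for orientation of the heart and a PET acquisition of 4-5 scans of about 20 minutes is started". The second follows it: "Thereafter a whole body (head to upper thighs) low dose CT scan is made for anatomical orientation and for attenuation correction".

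**Risk.** For 44.7 mSv, Section 3.4.3 states that "this corresponds to a lifetime risk of a fatal malignancy of about 1 in 600". Appendix 9 applies 5.5% per Sv to about 44 mSv and gives roughly 1 in 400 for a healthy adult. It says the patients' shorter life expectancy lowers this, but gives no adjusted number.

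**Eligibility.** Section 3.4.3 says that subjects with occupational or research exposure "in excess of 10 mSv above background over the previous three-year period" are excluded and that exposure is asked about at screening. Section 6.2 lists exclusions 1 to 32, and none sets a limit on prior radiation.

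**The concern.** Three radiation statements in the protocol disagree with other parts of it. The sum behind 44.7 mSv leaves out CTs that the protocol's own scanning procedure makes, so the words maximum and ceiling are not supported. The risk table shows a lower fatal-cancer risk than Appendix 9, for practically the same dose, with no reason given. A stated radiation safeguard never reaches the list against which eligibility is judged.

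Participants are not expected to benefit (Sections 3.4.4 and 3.4.5), so the dose and risk figures form part of the justification for exposing them. On eligibility, a person could satisfy every item in Sections 6.1 and 6.2 and still be someone whom Section 3.4.3 says is excluded. SAP Section 4.1 builds the listing of eligibility deviations from the inclusion/exclusion page of the eCRF. A rule absent from the criteria would not be expected to show up there.

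**Working it through.** **1. Reproduce the stated dose.** Inputs from Section 3.4.2 and Appendix 9: 37 MBq, 0.53 mSv/MBq, three CTs at 0.5 mSv per session, two sessions, PiB 1.5 mSv, two WAT scans at 0.5 mSv.

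- 89Zr per session: 37 × 0.53 = 19.61 mSv
- Session with three CTs: 19.61 + 3 × 0.5 = 21.11 mSv
- Total: 2 × 21.11 + 1.5 + 1.0 = 44.72 mSv

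This is the stated 44.7, and the three whole-body CTs per session use up the whole CT allowance.

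**2. Count the CTs.** Section 9.6.1 has one heart CT and one whole-body CT in the procedure, so a three-scan session has six CTs, of which three are counted. Two passages support a heart acquisition at every visit. Section 10.3.6 expects three SUV values per heart region from the three PET scans, and Section 10.3.7 takes the heart positions only from the dedicated heart scans.

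**3. Add the heart CT.** Its dose d is not given. I assume 0.1 to 0.5 mSv, with the protocol's own 0.5 mSv per CT as the upper end.

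| Subject | Sum without heart CT (mSv) | Heart CTs | d = 0.1 | d = 0.25 | d = 0.5 |
|---|---|---|---|---|---|
| First two in Part A (three scans, two sessions) | 44.72 | 6 | 45.3 | 46.2 | 47.7 |
| Third in Part A (two scans, two sessions) | 2 × (19.61 + 1.0) + 2.5 = 43.72 | 4 | 44.1 | 44.7 | 45.7 |
| Part B (two scans, one session; PiB and one WAT assumed) | 19.61 + 1.0 + 1.5 + 0.5 = 22.61 | 2 | 22.8 | 23.1 | 23.6 |

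Alternative cases for the first two Part A subjects:

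- Heart CT only at the first visit of each session: 44.72 + 2d = 44.9 to 45.7 mSv.
- No PiB or WAT: 42.22 + 6d = 42.8 to 45.2 mSv, above 44.7 only if d > (44.7 − 42.22)/6 = 0.41.
- Counted dose reduced to the 44 mSv aim: above 44.7 only if d > (44.7 − 44)/6 = 0.12 with six heart CTs, or 0.7/2 = 0.35 with two.

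The repeat CT after repositioning would add to any of these.

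**4. Risk at 5.5% per Sv**, as 1 in 1/(dose in Sv × 0.055):

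- 44 mSv: 1/(0.044 × 0.055) = 1 in 413
- 44.7 mSv: 1/(0.0447 × 0.055) = 1 in 407
- 47.72 mSv: 1/(0.04772 × 0.055) = 1 in 381

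The first two agree with Appendix 9. Reaching 1 in 600 would need (1/600)/0.0447 = 3.73% per Sv at the stated dose, or 1/(600 × 0.055) = 0.0303 Sv (30.3 mSv) at the stated coefficient. The documents give neither. Parts of the dose sum do not produce it either: one session (21.11 mSv) gives 1 in 861, and the 89Zr from both sessions alone (39.22 mSv) gives 1 in 464.

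**5. Eligibility, side by side.** The radiation row of the Section 3.4.3 table has three limits on who may enter. The lower age limit of 65 is in Section 6.1 (criterion 1), and childbearing potential is in Section 6.1 (criterion 3b). The 10 mSv limit is in neither 6.1 nor 6.2. The closest item, exclusion 25, concerns investigational treatment within 6 months or five half-lives and sets no radiation threshold.

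**The case against.** Section 9.6.1 does not say in terms that the heart CT is made at every visit. It narrates one procedure, beginning from the wait before the first scan, and leaves further detail to an imaging manual that is not available here. The heart-CT dose is unknown, only the first two Part A subjects have three scans per session, and the 44 mSv aim leaves some margin. SAP Section 2.2 says the WAT scans were not done and the PiB scan is not being done, which lowers real exposure. These points stand as limits on size. They do not rescue the stated maximum: the protocol's sum plans for PiB, WAT and the full 37 MBq, and on that basis even two heart CTs take it past 44.7 mSv. The sum also counts three whole-body CTs per session from the same single narration.

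On risk, 1 in 600 may include an allowance for age or shortened life expectancy. Appendix 9 says the risk is lower for these patients, and Section 3.4.2 gives the age and prognosis argument. That is possible, and the direction fits. But the risk table states no adjustment, and Appendix 9 offers no adjusted figure to match.

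On eligibility, the rule does exist in the protocol, with a question at screening. That makes it a failure to carry the rule across, not a missing idea. It still leaves the criteria list incomplete.

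Finally, the justification also rests on the severity of the disease and on image quality, and the protocol names no regulatory limit that 45 to 48 mSv would breach. This is fair, and it is why the point concerns the accuracy of stated safety figures rather than a demonstrated hazard.

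**Conclusion.** The concern holds in all three parts. On the protocol's own inputs the total for the first two Part A subjects is 44.72 + 6d mSv, an increase of 0.6 to 3.0 mSv (at most 3.0/44.72, about 7%) over the assumed range for d. This rests on a heart CT at each 89Zr PET visit, which is the natural reading of Section 9.6.1. The risk table's 1 in 600 is about one third lower than the 1 in 407 that follows from 44.7 mSv at 5.5% per Sv (407/600 = 0.68), with no reason stated. The 10 mSv exclusion is absent from Section 6. The consequences are modest, but the figures and the criteria list are wrong as written and should be corrected.

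**What to change.** - Recount the CT acquisitions in Section 9.6.1, state the heart-CT dose, and restate the total in Sections 3.4.2, 3.4.3 and 3.4.5 and in Appendix 9. Either include the repeat CT that Appendix 9 permits, or describe the figure as expected and drop maximum and ceiling.
- In Section 3.4.3, replace 1 in 600 with about 1 in 400, or state the age or life-expectancy adjustment that produces it.
- Add the prior-exposure criterion (more than 10 mSv above background from occupational or research sources in the previous three years) to Section 6.2.

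The cost is a text amendment. The declared dose rises slightly, the risk figure may look less favourable, and the added criterion could exclude a few candidates. The scanning procedure does not change.

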### **9.6.2. Cardiac Magnetic Resonance (CMR) Imaging**

Subjects will be asked to refrain from alcohol, caffeine, and nicotine on the days of CMR exams. Each baseline enhanced CMR imaging session will take approximately 45-60 minutes, with a maximum scan time inside of the scanner of approximately 90 minutes. If a scanning failure occurs, there will be a minimum of 24 hours prior to rescan.

As far as it is practicable, the local study site will use the same CMR imaging sequences, software acquisition, and contrast agent (i.e. DotaremTM) that is currently being used in the Phase 2 trial.

**Whenever possible, the baseline contrast enhanced MRI scan will be performed after a subject has passed other eligibility requirements.**

For each subject, if follow-up CMR examination(s) are clinically indicated for evaluation of potential cardiac adverse event(s) the same scanner as to the one used at the baseline examination should be used wherever feasible. Further details of site training and qualification procedures, and scanning protocols are provided in a dedicated Image Acquisition Manual to ensure consistency across study sites. Additional exploratory CMR endpoints, as detailed in the Imaging Acquisition Guidelines, may also be acquired for exploratory purposes.

All CMR scans will be reviewed at the local study site for disease and potential anti-SAP mAb-related clinical abnormalities.

However, image analysis for key CMR parameters which might be determinant for  $^{89}\text{Zr}$ -GSK2398852 myocardial uptake (e.g. extracellular volume [ECV] and myocardial perfusion) will be performed by a qualified imaging laboratory.

### **9.6.3. Access to Historical Patient ATTR-CM Cardiac Imaging**

Since it is likely that ATTR-CM subjects on enrolment into this PET study have had previous cardiac imaging, possibly including 2D-ECHO, CMR, bone tracer SPECT, and / or PET imaging (e.g. PiB or WAT), either at diagnosis and / or at follow-up, the images from these investigations and their respective reports should be available to GSK wherever feasible.

Availability of this patient data would enable a more comprehensive evaluation of  $^{89}\text{Zr}$ -GSK2398852 cardiac uptake in relation to cardiac amyloid load and myocardial coronary microvessel function.

## **9.7. Additional Assessments**

### **9.7.1. Access to Diagnostic Patient Cardiac Biopsy Tissue**

Where a ATTR-CM subject has had a cardiac (endomyocardial) biopsy, as part of a previous diagnostic workup, a sample of the tissue will be sent to GSK where possible. Routine and special histopathological investigations, including but not restricted to histochemical and / or immunohistochemical stains will be performed to assess for amyloid deposits and SAP levels, respectively.

## **9.8. Efficacy**

### **9.8.1. Safety/exploratory Biomarkers**

In the unlikely event of cardiac amyloid removal triggered by an anti-SAP mAb TMD(s) during this PET study, change in plasma NT-proBNP levels from baseline may provide surrogate biomarker evidence of cardiac amyloid clearance.

However, it is important that any reduction in plasma NT-proBNP levels are evaluated alongside any change in LV mass and / or ECV from any *repeat* CMR imaging which is performed at the local study site.

## **10. STATISTICAL CONSIDERATIONS**

### **10.1. Hypothesis**

This is an exploratory study where the primary objective is to assess cardiac uptake of  $^{89}\text{Zr}$ -GSK2398852 evaluated by PET imaging at different mass doses. No formal hypotheses will be tested as part of this study.

## 10.2. Sample Size Considerations

At the time of writing no empirical data was available to offer a suitable estimate for the expected between subject variability; therefore, the sample size has been determined primarily by feasibility.

A total of 6 subjects are expected to complete up to two dosing sessions. The study is split into two parts:

- in Part A up to 3 subjects will participate in up to two anti-SAP dosing sessions
- in Part B up to 3 subjects will participate in one anti-SAP dosing session.

Data will be reviewed in-stream with a view to inform subsequent unlabelled anti-SAP mAb mass dose levels.

### 10.2.1. Sample Size Re-estimation or Adjustment

No sample size re-estimation is planned for this study; however, at the interim (i.e. at completion of Part A) the team may decide to stop the study early and not recruit any subjects into Part B

## 10.3. Data analysis considerations

Statistical analyses will be performed by, or under the direct auspices of Clinical Statistics, GSK.

### 10.3.1. Populations for Analyses

For purposes of analysis, the following populations are defined:

- **All Treated Population:** defined as all subjects who receive at least one Anti-SAP treatment including  $^{89}\text{Zr}$ -GSK2398852. All safety analyses will be evaluated on this analysis population.
- **The PK Population:** defined as all subjects from the All Treated Population for whom a PK sample is obtained and analysed.

Additional analysis populations may be defined in the Reporting and Analysis Plan (RAP).

### 10.3.2. Interim Analyses

Decision making for the development programme is time critical and therefore there are two types of interim analysis planned in this study:

- **In-stream data review(s):** any emergent PET imaging data from the current study will be complementary to the ongoing phase II study (Study Number 201464) and its associated interim(s), as well as the broader Anti-SAP program. In addition, during the current study, changes may be made to a number of design

parameters based on the emerging data, including: (i) intra and inter mass dose levels; and (ii) the timing of PET scan, all based on the accruing data.

- **Interim analysis at the end of Part A:** once the last subject in Part A has completed their final dosing session, a formal review of all available safety data (including AEs, clinical laboratory data, vital signs, ECGs), PK, ECHO/CMR and PET imaging data will be conducted before deciding whether to trigger Part B.

### 10.3.3. Inter-Subject Reproducibility of Zr-GSK2398852 Myocardial Uptake

In any one subject in Part A, where the radiolabel PK and cardiac SUV profile of Zr-GSK2398852 is consistent with myocardial uptake during either the 1st or 2nd dosing session (i.e. cardiac / plasma SUV ratio  $\geq 0.5$ ), the reproducibility of this specific unlabelled anti-SAP mAb dose in enabling myocardial uptake of Zr-GSK2398852 may be evaluated by treating further subjects with the same unlabelled anti-SAP mAb mass dose. This is an optional evaluation that is at the discretion of the Investigator or designee in consultation with the Medical Monitor (Figure 7, below).

[figure not shown]
### 10.3.4. Intra-subject confirmation of Zr-GSK2398852 Myocardial SAP Binding

In any one subject in Part A where the radiolabel PK and cardiac SUV profile of Zr-GSK2398852 is consistent with myocardial uptake during the 1st dosing session (i.e. cardiac / plasma SUV ratio  $\geq 0.5$ ), Zr-GSK2398852 binding to myocardial SAP can be confirmed by performing an *intra*-subject mAb displacement evaluation.

This will be attained by escalating the unlabelled anti-SAP mAb dose in the same subject on their 2nd dosing session (provided the AE profile from the 1st dosing session is acceptable) to evaluate whether a higher unlabelled anti-SAP mAb mass dose can attenuate the cardiac SUV signal compared to their 1st dosing session; this would be indicative of displacement of Zr-GSK2398852 from SAP binding sites on amyloid myocardial deposits.

This is an optional evaluation that is at the discretion of the Investigator or designee in consultation with the Medical Monitor (Figure 7, below).

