### 3.2.2. Radiolabelled Anti-SAP mAb: 89Zr-GSK2398852

PET has been selected as the imaging modality for this because it provides sufficiently high spatial resolution (about 6 mm) and a high sensitivity and ability for accurate quantitation of radioactivity concentration throughout the body.

There are several positron emitting radionuclides which are used for human PET studies, but for a study like the one proposed here, the half-life of the radionuclide is a key selection factor. O (2 minutes), C (20 minutes), Ga (68 minutes), and F (2 hours) are frequently used in PET, but these short half-lives would not allow recording of biodistribution of labelled antibodies with plasma elimination half-lives of multiple hours to days and very slow anticipated penetration to the extracellular space. Zr with a half-life of 3.2 days is suited for such studies since it allows a more comprehensive evaluation of tissue biodistribution of the radiolabelled antibody for longer than two days.

A further advantage of Zr is that generic labelling methods have been developed whereby antibodies can be labelled in a standardized procedure and with the binding and

distribution properties retained [Dijkers 2009, Perk 2010, Gaykema 2013, Menke-van der Houven van Oordt CW 2015, Pedit-Taskar 2014, Pedit-Taskar 2015, Laforest 2016].

GSK2398852 (anti-SAP mAb) has been conjugated to Zirconium (Zr) using a non-cleavable linker (See Supplement to Investigator Brochure for GSK2398852 + GSK2315698, GlaxoSmith Kline Document Number 2017N343159\_00).

In vitro experiments have shown that the binding affinity of the Fab domain of Zr-GSK2398852 for SAP is similar to unlabelled anti-SAP mAb which has been therapeutically used in combination with CPHPC in the FIH study (SAP115570). In contrast, the Fc domain of Zr-GSK2398852 has been shown in vitro to have an approximate 30% reduction in C1q binding which could lead to a potential reduction in immunological effector function. Thus the small dose of Zr-GSK2398852 (10 mg) is unlikely to substantially contribute pharmacology whether beneficial or adverse.

The local vascular distribution, tissue permeability, and PK profile of Zr-GSK2398852 in the myocardium of ATTR-CM patients is predicted to be dependent upon five factors:

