### 3.4.4. Benefit Assessment

The purpose of this study is to provide an assessment of the myocardial uptake of anti-SAP mAb using a radiotracer technique. Unlabelled anti-SAP mAb is also given because the ratio of tracer to total body amyloid is low. In order to minimise the risk of dose-dependent adverse effects the maximum total dose of anti-SAP mAb has been capped at 500 mg. In the first in human study the lowest dose associated with objective evidence of amyloid removal (in the liver) was 246 mg in a single subject. Thus the doses of anti-SAP mAb given in this study have the potential to be pharmacologically active and to trigger amyloid removal however they are low and are not expected to result in therapeutic removal. Thus participants in this study are not expected to derive direct therapeutic benefit but the information from this and the ongoing phase 2 study will be combined to inform rational dose selection for future development.

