## **5.9. Length of Time Between Dosing Sessions**

There must be a minimum of 4 weeks between each dose of anti-SAP mAb, to allow for plasma SAP levels to return to baseline.

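### The displacement check in Protocol 10.3.4 selects on a high Session 1 ratio, always gives the higher dose second and sets no minimum fall, so a fall in cardiac SUV cannot by itself confirm SAP binding

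*Protocol*

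**What the plan says.** Protocol 10.3.4 applies to any Part A subject whose Session 1 profile is taken to show myocardial uptake, defined by a threshold of 0.5 ("i.e. cardiac / plasma SUV ratio"). The procedure is: "This will be attained by escalating the unlabelled anti-SAP mAb dose in the same subject on their" second dosing session, in order "to evaluate whether a higher unlabelled anti-SAP mAb mass dose can attenuate the cardiac SUV signal compared to their" first session. If the signal is lower, "this would be indicative of displacement of" the tracer from SAP sites on myocardial amyloid. The section heading, its opening sentence and the Figure 7 legend all use the language of confirmation. The check is discretionary: "This is an optional evaluation that is at the discretion of the Investigator or designee in consultation with the Medical Monitor".

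The interval between sessions is set in Protocol 5.9: "There must be a minimum of 4 weeks between each dose of anti-SAP mAb, to allow for plasma SAP levels to return to baseline". No other reason for its length is given there.

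The SAP adds no rule for this check. Section 7.1.2 carries forward the between-subject reproducibility evaluation of Protocol 10.3.3 but not 10.3.4. Section 2.2 drops descriptive statistics for PET endpoints and reports that the blood-flow (WAT) scans were not done. PET analysis is unblinded (Protocol 7.4).

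**The concern.** Within the check, the higher dose is always the second session, so anything that differs between sessions is confounded with dose. Two ordinary causes of a lower second reading need no displacement. One is session-to-session noise: with no minimum fall, any decrease qualifies. The other is regression to the mean, because subjects enter on the strength of a high first reading. The plan offers nothing to set against these: no test-retest estimate, no same-dose repeat within a subject, no reversed order. The WAT scan planned for Session 2, which could have shown a change in blood flow, is also gone.

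At most three subjects can contribute. One pair could therefore carry a mechanistic statement, and Protocol 10.3.2 says the PET data will complement the Phase 2 study and the wider programme.

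**Working it through.** The plan gives no power, effect size or variance to reproduce. Sample size is set by feasibility (Protocol 10.2), no hypothesis is tested (10.1), and no between-subject estimate existed. The variances below are assumptions.

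**1. Residual tracer and plasma antibody at 28 days.** Residual fraction = 0.5^(28 days / half-life).

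- ⁸⁹Zr, "with a half-life of 3.2 days is suited for such studies" (Protocol 3.2.2): 28/3.2 = 8.75 half-lives; 0.5^8.75 = 0.0023, or 0.23%. Leftover tracer would raise the second reading, not lower it.
- Plasma mAb, terminal half-life about 15 h at 80 mg (5.13.1): 28 × 24/15 = 44.8 half-lives; 0.5^44.8 ≈ 3 × 10⁻¹⁴. Clearance is expected to be slower than this at higher doses (5.13.1). For 1% to remain, the half-life would have to be 28 × ln 2 / ln 100 = 4.2 days.
- Tissue-bound antibody: no half-life is given. As an assumption, 6.5, 8.4 or 12.1 days would leave 5%, 10% or 20%.

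**2. Chance of a fall when dose has no effect.** Let log(true ratio) be Normal(log m, 0.3²), with independent Normal(0, s²) errors in the two sessions. Keep subjects with Session 1 ≥0.5 and compute P(Session 2 < Session 1), using 2,000,000 draws per setting.

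| Median true ratio m | s = 0.10 | s = 0.15 | s = 0.20 |
|---|---|---|---|
| 0.4 | 0.62 | 0.66 | 0.70 |
| 0.5 | 0.57 | 0.60 | 0.63 |
| 0.6 | 0.54 | 0.56 | 0.58 |
| 0.8 | 0.51 | 0.52 | 0.53 |
| 1.0 | 0.50 | 0.51 | 0.51 |

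With no selection the value is 0.50 for any s, and all three of three subjects fall with probability 0.5³ = 0.125. In the selected settings that becomes 0.54³ = 0.16 to 0.70³ = 0.34.

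**3. Larger falls.** For medians 0.4–0.6, a fall of 15% or more occurs in about 15–46% of selected subjects. Most of this is session noise, not selection. Without selection the probability is Φ(ln 0.85 / (√2·s)): for s = 0.10, Φ(−0.1625/0.1414) = 0.13; for s = 0.20, Φ(−0.1625/0.2828) = 0.28.

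**4. Sensitivity.**

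- Wider assumptions (medians 0.3–0.5, between-subject CV 30–50%, within-subject CV 10–30%): a fall in 55–83%.
- Selection on the ratio but read-out on cardiac SUV, with error split equally between heart and plasma (medians 0.3 and 0.5, between-subject CV 30%, within-subject CV 10–30%): 55–74%.
- If the higher dose raised uptake by 10% (assumed) without displacement, the 54–70% in step 2 would become 28–56%.

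**The case against.** Several points on the other side stand. The check is optional, exploratory and limited to Part A. The operative sentence says indicative, not proven. Selection matters little if true ratios lie well above 0.5. The table uses one variable for both selection and read-out, whereas 10.3.4 selects on the ratio and reads cardiac SUV. Its null is no dose effect, while 5.13.1 expects a higher total mass dose to slow clearance and increase interstitial uptake. A fall against that expectation is more informative than the table implies.

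A reader might also infer three stronger things that the documents do not support.

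- *That carry-over would be mistaken for SAP binding.* Tracer and plasma antibody are essentially gone by 28 days. Protocol 3.4.4 does say the doses "have the potential to be pharmacologically active and to trigger amyloid removal", but the same sentence adds that they are low and not expected to give therapeutic removal. Its only removal example is one subject's liver at 246 mg. Antibody still on cardiac SAP, or amyloid removed by antibody, would itself require binding in the heart (3.4.3, myocarditis row). That route credits the fall to the wrong session; it does not fake binding.
- *That this is the only within-subject evidence of binding.* The mechanistic model in Protocol 10.3.6 and SAP 9.1.3 separates a bound component for each subject and mass dose. The 0.5 limit in 10.3.7.1 is also a per-subject indicator.
- *That unselected pairs would be hidden.* Protocol 10.3.5 lists all data, and SAP 12.9.6 and 12.9.12 plot and list the PET parameters.

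What remains is the inference: 10.3.4 gives any fall, in a selected subject and a fixed order, a meaning it cannot carry alone.

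**Conclusion.** The concern holds for noise, selection and fixed order; carry-over is secondary. If the higher dose did nothing, a fall would be seen in 54–70% of selected pairs with true ratios centred on 0.4–0.6, and in 50–53% with ratios centred on 0.8–1.0. Both ranges assume a between-subject log-SD of 0.3 and a session log-SD of 0.10–0.20, which the documents neither give nor contradict. Both would be lower if the higher dose raises uptake. Even at 50%, a fall of unspecified size in one to three subjects is weak support for a statement that binding is confirmed. Possible tissue-level carry-over leaves uncertain which session's dose caused a fall. The primary PET listings are unaffected; the issue is the mechanistic conclusion drawn from them.

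**What to change.** In Protocol 10.3.4 and the Figure 7 legend, replace the confirmation wording with a statement that a fall may be consistent with displacement. Then, in the protocol or SAP:

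1. Name the read-out and scan in advance: plasma-adjusted, at matched times in both sessions. Protocol 10.3.7.1 already says tissue SUV must be related to plasma radio-PK.
2. Require a fall larger than a stated session-to-session limit before using the displacement wording. For illustration, a one-sided 95% limit of 1 − exp(−1.645·√2·s) is 21% for s = 0.10, 29% for 0.15 and 37% for 0.20. The source of s must be stated, since neither document supplies one. Otherwise report attenuation, with dose and session effects not separated.
3. Beside each pair, show Day 1 pre-dose plasma SAP for both sessions and the Session 2 pre-infusion mAb concentration. Flag pairs that have not returned to Session 1 pre-dose values. These are plasma checks and do not measure tissue occupancy.
4. Interpret all escalated Part A pairs together, not only those that met 0.5 in Session 1.
5. Treat a first exposure at the higher dose in another subject as supportive only. Protocol 5.12.1.2 prefers within-subject comparison because amyloid load may differ greatly between subjects.

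The cost is wording and one combined display. The samples are already scheduled (Schedule of Activities and Protocol Table 4), and no subjects or scans are added. The downside is that fewer pairs will support a displacement statement. No dose or washout is prescribed here.
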